### 1.5.2.1. Previous Experience of Seribantumab in Metastatic Breast Cancer

Seribantumab was tested in combination with exemestane in a previous placebo-controlled Phase 2 study in post-menopausal patients with ER/PR+, Her2 negative breast cancer. Using a dose of seribantumab as determined from a Phase 1 dose escalation study, patients were randomized to receive 25 mg exemestane daily in combination with either 20 mg/kg weekly seribantumab (with a 40 mg/kg loading dose) (N=59) or placebo (N=59) as presented at the American Society of Clinical Oncology (ASCO) (Higgins et al., 2014). The primary efficacy objective of achieving a 50% reduction in hazard ratio in the Seribantumab group vs. the placebo group was not reached. The estimated median PFS was 15.9 weeks for the seribantumab group vs. 10.7 weeks in the placebo group, resulting in a hazard ratio of 0.772 (p=0.2486).

A pre-planned biomarker analysis using archived tissue samples obtained from patients enrolled in the study showed that patients who had HRG positive tumors (as determined by RT-PCR testing) had an increased risk of progression when receiving exemestane alone in comparison to those patients who had HRG negative tumors. Patients with HRG positive tumors seemed to benefit from the addition of seribantumab to exemestane. These data are described in detail in Section 1.4.

Additionally, seribantumab was tested in combination with paclitaxel in a previous Phase 2 study in patients with either locally advanced, pre-operative hormone receptor positive and Her2 negative breast cancer (N=101). Patients were randomized to receive either a 2- week run-in of

seribantumab followed by 4 weeks of weekly seribantumab in combination with paclitaxel or 4 weeks of weekly paclitaxel alone. Both groups of patients were then treated biweekly with 4 cycles (8 weeks) of doxorubicin in combination with cyclophosphamide and subsequently underwent surgery. The primary efficacy readout was pathologic complete response rate (pCR). Patients on the Seribantumab arm had a pCR rate of 10.1% (7/66) and patients on the control arm had a pCR rate of 3.3% (1/33). No formal hypothesis testing was done in this study.

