# 1.5.3.1. Previous Safety Experience of Seribantumab in Combination with Endocrine Therapies

Seribantumab has been combined with exemestane in one previous placebo-controlled study, and 56 patients were dosed with the combination. In this study, the most frequently reported adverse events (reported in  $\geq$ 15% of patients) regardless of relationship included (treatment arm % vs. control arm %): diarrhea (50.0% vs 23.7%), nausea (28.6% vs 23.7%), fatigue (25.0% vs 23.7%), arthralgia (21.4% vs 20.3%), cough (16.1% vs 16.9%), and decreased appetite (16.1% vs 10.2%). The most frequently reported adverse events (reported in  $\geq$ 15% of patients) that were assessed by the Investigator to be related to seribantumab include: diarrhea (37.5% vs 11.9%), fatigue (19.6% vs 13.6%), and nausea (16.1% vs 18.6%).

[figure not shown]
Serious adverse events were reported in 7 patients (12.5%) on the seribantumab plus exemestane arm compared to 11 patients (18.6%) on the control arm. The most frequently reported serious event on the seribantumab containing arm was nausea, occurring in 2 patients (3.6%).

Seribantumab has not been combined with fulvestrant in other clinical studies. It is expected that seribantumab will continue to combine well with endocrine agents and with no expected increases in frequencies of severe or serious adverse events. Increased reports of mild to moderate AEs may be observed for diarrhea, nausea, vomiting, and fatigue.

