#### 7.7. Disease Evaluation

Tumor response will be evaluated by the local radiologist according to the Response Evaluation Criteria in Solid Tumors (RECIST) version 1.1 (Eisenhauer et al., 2009) to establish disease progression by CT or MRI. In addition, other radiographic or scintigraphic procedures (such as radionuclide bone scans), as deemed appropriate by the investigator, will be performed to assess sites of neoplastic involvement. The same method of assessment must be used throughout the study. Please refer to image acquisition guidelines for the requirements for image collection and scanner qualification. Investigators should choose target and non-target lesions in accordance with RECIST v1.1 guidelines. Follow-up measurements and overall response should also be in accordance with these guidelines. To be assigned a status of confirmed partial response (PR) or complete response (CR), changes in tumor measurements must be confirmed by repeated assessments that should be performed ≥30 days after the criteria for response are first met.

Disease should be assessed every 8 weeks (±5 days) from randomization regardless of treatment schedule until investigator-assessed progression. In cases where there is a suspicion of disease progression prior to the next scheduled scan, an unscheduled assessment should take place. All patients who come off study treatment prior to disease progression for reasons including patient or physician decision or unacceptable toxicity will continue to undergo tumor assessments every 8 weeks (±5 days) until investigator-assessed progression of disease.

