#### 10.3. Analysis Populations

Patients that have signed informed consent, are identified as HRG positive based on centralized tissue analysis, and have successfully completed study entry criteria will be delineated into the following analysis populations:

- **Intent-to-Treat (ITT) population**: This population includes randomized patients. Patients will be analyzed in the randomized group.
- **Per Protocol (PP)**: This population includes randomized patients. Patients will be analyzed in the randomized group. The PP population is the primary efficacy population and will only include patients that meet inclusion/exclusion criteria as defined in Section 4.1 and 4.2 and are confirmed HRG positive based on the prospective fresh centralized tissue analysis (pre-treatment tissue sample).
- Safety (SAF) population: The safety population includes patients receiving at least one dose of study medication. All safety analyses will be performed on this population.
- **PK population**: All treated patients with at least one PK assessment.

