## 2. Analysis Sets

## 2.1 Intent-to-Treat (ITT)

The ITT population will include all patients who are randomized, with study drug assignment via an Interactive Web Response System (IWRS), irrespective of whether patients receive the intended study drug or a different drug than

allocated through randomization. ITT patients with central lab HRG positive (1+, 2+, 3+, 4+) results will be considered the primary efficacy population. Patients with missing or indeterminate HRG or HRG negative will not be part of the ITT primary efficacy population.

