## **3. ENDPOINTS**

## 3.1 Progression-Free Survival – Investigator Assessed

Investigator Assessed (IA) tumors assessments are those determined by the investigator. PFS is defined as the number of months from the date of randomization to the date of death or documented (objective) disease progression via RECISTv1.1, whichever occurs earliest. Length of PFS will be calculated in days and reported in months.

[Progression/Death/Censor Date - Randomization Date + 1] / 30.4375.

The tumor assessment (i.e., scan dates) will be used for progression/censor date not the date corresponding to the determination of overall response. When multiple dates occur for assessing target, non-target, and new lesions the following rule will be applied:

- If documented disease progressions, the *first* available date will define the tumor assessment date
- If censored, the *last* available date will define the tumor assessment date.

Per protocol tumor assessments are scheduled to be performed every 8 weeks ( $\pm$  7 days) from day of first dose until investigator-assessed progression, in addition to a 30-day follow-up.

**Censorship**: In general, patients are censored at the date of the last tumor assessment that verified lack of disease progression if they are last known to be alive, on-treatment or within 30 days following treatment discontinuation, and progression-free. Censoring is explicitly described below and in table 1. Patients that do not experience progression or death by the time of analysis (data cut-off) will be censored at the date of last tumor assessment defined by any overall response other than "not evaluable".

- Patients with an inadequate/incomplete baseline tumor assessment will be censored at the date of randomization
- Patients with no tumor assessment after dosing will be censored at the date of randomization unless death occurred prior to the first planned assessment (in which case the death is an event)
- Patients with at least one on-study disease assessment who discontinue treatment without documented disease progression or death are censored at the date of the last tumor assessment

There are two exceptions.

- $\circ$  Documented progression or death  $\leq$  30 days after treatment discontinuation then progression or death is an event

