#### Table 3.1 Documented Disease Progression and Censoring

Situation	Date of	Outcome
Inadequate baseline tumor assessment No on-treatment assessment and no death prior to first scheduled assessment	Randomization	Censored
Death or documented disease progression after ≥ 2 consecutively missed and/or not evaluable scheduled tumor assessments	Last tumor assessment documenting no disease progression	Censored
Alive, on-treatment, and no documented disease progression	Last tumor assessment documenting no disease progression	
Documented disease progression (on, prior to, or $\leq 30$ days after treatment discontinuation)	First tumor assessment documenting disease progression	Progression (Event)
New anticancer treatment $\leq$ 30 days after treatment discontinuation without disease progression	Last tumor assessment documenting no disease progression prior to starting the new anticancer treatment	Censored
Treatment discontinuation due to toxicity, undocumented disease progression, or any other reason	Last tumor assessment documenting no disease progression prior to discontinuation	Censored
Death prior to first scheduled assessment	Death	Death (Event)
Death without documented disease progression and $\leq 30$ days after treatment discontinuation	Death	Death (Event)

Note: Follow-up scans can be performed up to 4 weeks from last treatment dose date via protocol

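### Read literally, the SAP's censoring rule drops a documented progression in a randomized, never-dosed patient from the primary PFS, which contradicts its own endpoint and analysis sets; the effect is small

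*SAP*

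**What the plan says.** The Censorship part of SAP 3.1 reads: "Patients with no tumor assessment after dosing will be censored at the date of randomization", except where the patient died before the first planned assessment; such a death is an event. Table 3.1 restates the row as "No on-treatment assessment and no death prior to first scheduled assessment", dated at randomization and censored. The table's progression row counts an event by reference to when treatment was discontinued.

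Elsewhere, dosing is not a condition:

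- SAP 3.1 opens by defining PFS as the time from randomization to death or documented RECIST progression, whichever is earlier.
- SAP 2.1 puts every randomized patient in the ITT set "irrespective of whether patients receive the intended study drug". Its primary efficacy set adds only a positive central HRG result.
- Protocol 10.3 begins both its ITT and its PP definition with "This population includes randomized patients. Patients will be analyzed in the randomized group". PP adds eligibility and HRG positivity on fresh tissue, but not dosing.
- The protocol synopsis (statistical considerations) censors at randomization only for lack of a valid tumor evaluation at randomization.

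The scan anchor is not consistent. Protocol 7.7 schedules disease assessment every 8 weeks "from randomization regardless of treatment schedule until investigator-assessed progression", and the synopsis and Protocol 3.1 agree. The schedule table in Protocol 6.1 and SAP 3.1 count from first dose.

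**The concern.** Protocol 3.1 allows up to 7 days between randomization and first dose, so a patient can be randomized and never treated. Such a patient belongs to the SAP ITT set and, if the HRG and eligibility conditions are met, to the primary efficacy set of either document. The censoring rule then keeps the patient in the analysis but contributes zero follow-up, whatever the scans show. What is at stake is whether the primary analysis uses the events of everyone it claims to analyze. If the patients affected were unevenly split between arms and had an unusual prognosis, the hazard ratio would shift.

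**Working it through.** **1. The rule applied to a randomized, never-dosed patient**

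| Outcome | SAP 3.1 opening definition | SAP 3.1 censoring rule and Table 3.1, read literally |
|---|---|---|
| Progression on a scan | Event on scan date | Censored at randomization |
| Death before first planned scan | Event | Event, but the SAP counts scans from first dose, so this date is undefined here |
| Later death, no scan after dosing | Event | Censored at randomization |

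The progression row does not clearly rescue the first case, because the patient has no treatment-discontinuation date.

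**2. The plan's event count (Protocol 10.2)**

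Inputs: HR 0.57, one-sided alpha 0.10, power 80%, 1:1. Schoenfeld: events = 4 × (1.2816 + 0.8416)² / (ln 0.57)² = 18.03 / 0.316 = 57.1, rounded up to 58. This reproduces the stated figure; power at 58 events is 0.805.

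**3. Events lost**

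Inputs from Protocol 10.2: 80 patients, accrual A = 16 months, total T = 20 months, medians 4 and 7 months. Assumed: exponential PFS, uniform accrual, no dropout. With λ = ln 2 / median, P(event) = 1 − [exp(−λ(T−A)) − exp(−λT)] / (λA).

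- Control: 1 − (0.5000 − 0.0313)/2.773 = 0.831
- Seribantumab: 1 − (0.673 − 0.138)/1.584 = 0.662
- Expected events: 40 × 0.831 + 40 × 0.662 = 59.7
- Average loss per censored patient: 59.7/80 = 0.75

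The number k of never-dosed patients is not in the documents; 0 to 5 is an assumed range.

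| k of 80 | Expected events at month 20 | Power at that count | Month in which 58 are expected |
|---|---|---|---|
| 0 | 59.7 | 0.813 | by 20 |
| 1 | 59.0 | 0.810 | by 20 |
| 2 | 58.2 | 0.806 | by 20 |
| 3 | 57.5 | 0.802 | 20.2 |
| 4 | 56.7 | 0.798 | 20.6 |
| 5 | 56.0 | 0.794 | 20.9 |

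The analysis is triggered by events, so the practical cost is a short delay rather than lost power.

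**4. Hazard ratio and type I error**

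Simulation: 40 v 40, 16-month uniform accrual, cut at 58 events, exponential PFS, unstratified Cox model, 4,000 to 6,000 trials per scenario. Each row compares counting all scans with applying the rule.

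| Assumed never-dosed (seribantumab v placebo) | Median HR | One-sided error under no effect (nominal 0.10) |
|---|---|---|
| 2 v 0, control-like risk | 0.59 to 0.57 (about 1.6 events dropped) | 0.103 to 0.104 |
| 1 v 1, median 1 or 2 months | unchanged | 0.10 to 0.10 |
| 2 v 0, median 1–2 months, with 2 equally poor-prognosis but dosed placebo patients | 0.59 to 0.54–0.56 | 0.10 to about 0.12–0.13 (0.11–0.14 across repeat runs) |

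**5. Is 2 v 0 supported?**

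In the earlier exemestane trial 59 were randomized per arm (Protocol 1.5.2.1) and "56 patients were dosed with the combination" (Protocol 1.5.3.1). The serious-event percentages agree: 7/56 = 12.5% and 11/59 = 18.6%, which implies that all 59 controls were dosed. So 3/59 (5.1%) v 0/59, and 40 × 3/59 = 2.0 patients here. The chance that all 3 of 118 fall in one named arm is C(59,3)/C(118,3) = 32,509/266,916 = 0.122; doubled, Fisher's two-sided p = 0.24.

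**The case against.** A reader might infer that the rule turns the comparison into an as-treated one and biases the hazard ratio toward seribantumab. The documents do not support that. Patients stay in their randomized arm; the effect is closer to leaving out the never-dosed. The trial is double-blind with placebo infusions, so loss before first dose cannot respond to knowledge of the arm, and an imbalance would arise by chance. The earlier 3/59 v 0/59 is compatible with chance. A reader might also infer that such a patient can never contribute an event, but the early-death exception rules that out. These objections stand and limit the point.

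Others stand in part:

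- The SAP may not govern this trial. SAP section 1 names protocol seribantumab-02-03-10, while the supplied protocol is MM-121-02-02-10, whose synopsis rules would count this progression. But Protocol 10.5.1 leaves censoring detail to the SAP, and this is the only one supplied.
- Sensitivity analyses cover part of this. SAP 5.5.2 treats seribantumab-arm censors as events on the censoring date, and Protocol 10.5.2 treats all censors as events. Neither restores the true progression date or corrects the primary analysis.
- Scans may not exist. The off-treatment scanning provisions describe patients who come off treatment, none names a never-dosed patient, and the Protocol 6.1 table counts from first dose. It is therefore not secure that the data would already be collected.
- The correction may recover little. If 80% of never-dosed patients start another therapy (an assumption), the error in the adverse 2 v 0 case is 0.122–0.128 with the correction and 0.129–0.139 without it.

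**Conclusion.** The point holds as a narrow contradiction. Taken at its words, the SAP discards documented progressions, and some deaths, in patients whom its own endpoint definition and analysis sets include. The cost is about 0.75 to 0.8 events per such patient. For 1 to 5 such patients, power is 0.810 to 0.794, against 0.813 with none. A shift in the median HR from about 0.59 to 0.57 needs an assumed 2 v 0 split. Error inflation to about 0.12–0.13 needs both that split and a median PFS of 1 to 2 months in those patients. The documents give neither the number, the balance nor the prognosis of never-dosed patients, so systematic bias is not established. The wording should still be corrected, because the primary analysis should follow its stated population.

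**What to change.** - In SAP 3.1 replace *after dosing* with *after randomization*. In Table 3.1 replace *No on-treatment assessment* with *No post-randomization assessment*.
- Add one sentence: progression or death in a randomized, never-dosed patient is a PFS event on its date, subject to the same new-therapy and missed-scan censoring as for other patients. It is needed because the table's other rows depend on a treatment-discontinuation date.
- Keep the early-death exception, and count the first planned assessment from randomization.
- Reconcile the scan anchor: first dose in the Protocol 6.1 table and SAP 3.1, randomization in the synopsis, Protocol 3.1 and 7.7.
- Carry the wording into the SAP that governs MM-121-02-02-10.

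The cost is a few words in the SAP and alignment of the scan schedule text. The required 58 events do not change. Few events will be recovered where never-dosed patients start other therapy or are not scanned.

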on the date of randomization. Patients starting a new anti-cancer treatment prior to documented PD will be censored at the date of the last observed tumor assessment prior to start of the new treatment. Patients with documented PD or death after an unacceptable long interval (i.e., 2 or more missed or indeterminate scheduled assessments) will be censored at the time of the last observed tumor assessment date. PFS will be calculated as the date of the event/censor minus date of randomization plus one.

The primary analysis will be performed using a stratified log-rank test comparing the PFS difference between two treatment arms. The final PFS analysis will preserve the 1-sided alpha at 0.10. Stratification factors will include bone-only disease (yes, no) and geographic status (US, and non-US). Kaplan-Meier estimates will be used to display PFS time graphically. Cox proportional hazards model will be used to estimate hazard ratio and the corresponding 80% confidence interval. Median PFS event times and 80% confidence interval will be computed as well.

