### Arm B (Comparator Arm):

- Placebo: intravenously (IV) on days 1 and 15 of each 28-day cycle
- Fulvestrant: 500 mg IM on days 1 and 15 of Cycle 1, and on day 1 of each subsequent 28 day cycle

Treatment must start within 7 days following randomization. It is intended that patients will be treated until investigator-assessed disease progression or unacceptable toxicity, whichever comes first. Tumor assessments will be measured and recorded by the local radiologist every 8 weeks (+/- 5 days) from randomization using the RECIST guidelines (version 1.1). Tumor assessments will be performed every 8 weeks regardless of dose delays or dose interruptions, until investigator-assessed progressive disease. Patients who come off study treatment prior to disease progression, for reasons including patient or physician decision or unacceptable toxicity, will continue to undergo tumor assessments every 8 weeks (±5 days) until investigator assessed PD. Patients will be treated according to local assessment of tumor scans, and the primary analysis will be conducted based on investigator assessments.

All patients will have a follow-up visit scheduled 30 days (±7 days) after the last dose of study treatment, regardless of reason for treatment termination. Patients will not be allowed to cross over from placebo to seribantumab.

Survival follow up will be required for all patients every 2 months from the 30-day follow-up visit until death, loss to follow-up, withdrawal of consent, or study termination. After patients discontinue study treatment, subsequent anti-cancer therapies will be collected at the same time as survival follow-up.

An independent data monitoring committee (DMC) will be established to monitor emerging safety data and evaluate for trial efficacy. The DMC will regularly monitor safety data over the course of the study in accordance with the DMC Charter.

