## **1. INTRODUCTION**

This is the Statistical Analysis Plan (SAP) for protocol seribantumab-02-03-10.

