## 5.5.2 PFS Sensitivity and Subgroup Analysis

PFS will be performed using a variety of methodology to assess the sensitivity to deviations and covariate factors. The same one-sided significance level at 0.025 will be used for all situations.

- Unstratified log-rank test will be performed and a Cox proportional hazards model with treatment only in the model to estimate the hazard ratio and 95% confidence intervals
- Treatment group comparison using interval-censored methods
- Evaluation of influences of baseline covariates and biomarker factors using stepwise selection methods
- Treat all censors on the seribantumab arm as events on the date of censorship
- Cox proportional hazard models will include treatment and covariate in the model. Additional models will include treatment, covariate, and the interaction effect in the model. Hazard ratios and 95% confidence intervals will be reported for all models. In addition, median event estimates and 95% confidence intervals will be reported. Forest plots of the hazard ratio estimates and confidence intervals will be displayed for the aforementioned models.

PFS will also be analyzed using IRR. PFS will be analyzed using a stratified Cox proportional hazard models similar to the primary analysis. Cox proportional hazard models will include treatment and covariate in the

model. Additional models will include treatment, covariate, and the interaction effect in the model. Hazard ratios and 95% confidence intervals will be reported for all models. In addition, median event estimates and 95% confidence intervals will be reported. Forest plots of the hazard ratio estimates and confidence intervals will be displayed with for the aforementioned models.

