#### Symptomatic/clinical progression

Subjects requiring discontinuation of treatment without objective evidence of disease progression should not be reported as PD on tumor assessment CRFs. Every effort should be made to document objective progression even after discontinuation of treatment.

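### The SAP stops counting PFS events 30 days after treatment ends, while the protocol keeps scanning for those events and counts them

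*SAP*

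**What the plan says.** **SAP.** Section 3.1 censors patients with at least one on-study assessment "who discontinue treatment without documented disease progression or death are censored at the date of the last tumor assessment". Progression or death after stopping is an event only if it occurs within 30 days of discontinuation. Table 3.1 repeats the rule in a row headed "Treatment discontinuation due to toxicity, undocumented disease progression, or any other reason", with outcome censored. The note under the table states: "Follow-up scans can be performed up to 4 weeks from last treatment dose date via protocol".

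**Protocol.** Section 10.5.1 and the Synopsis define PFS as time from randomization to RECIST v1.1 progression or death from any cause. The Synopsis names four reasons to censor: no event observed, no valid baseline evaluation, new therapy ("Patients starting a new anti-cancer treatment prior to documented PD will be censored at the date of the last observed tumor assessment"), and an event following at least two missed or unreadable scans. Stopping treatment is not among them. Section 3.1 says patients who stop early "will continue to undergo tumor assessments every 8 weeks (±5 days) until investigator assessed PD"; section 7.7 and footnote 5 of the section 6.1 schedule also require scans until progression.

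**Within the SAP.** Section 3.1 itself describes scanning until investigator-assessed progression, and the appendix on symptomatic progression says: "Every effort should be made to document objective progression even after discontinuation of treatment". The censoring rule then sets aside any such progression found after day 30.

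**The concern.** The two documents count different events for the primary endpoint. A patient who stops for toxicity, starts no other therapy and progresses on a scheduled scan eight weeks later is an event under the protocol and censored under the SAP.

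Two things are at stake:

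- **Information.** The primary analysis is triggered at 58 PFS events. If the 58 are counted under the SAP rule, the trial takes longer. If they are counted under the protocol definition and analysed under the SAP rule, the test runs on fewer than 58.
- **Bias.** Protocol section 4.4 lists clinical deterioration separately from RECIST progression as a reason to stop. Such patients fall in the Table 3.1 row that censors them, so censoring may be related to imminent progression. If this differs by arm, the hazard ratio is distorted. The direction cannot be predicted: in the earlier exemestane study (protocol 1.5.3.1), diarrhoea was more frequent on seribantumab (50.0% v 23.7%) but serious adverse events were less frequent (12.5% v 18.6%).

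No listed sensitivity analysis is stated to restore late events at their true dates. SAP 5.5.2 has "Treat all censors on the seribantumab arm as events on the date of censorship", and protocol 10.5.2 recodes all censored patients as events.

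**Working it through.** **1. The plan's own figure.** Protocol 10.2: HR 0.57 (medians 4 v 7 months), one-sided alpha 0.10, power 80%, 1:1.

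Events = 4(z₀.₉₀ + z₀.₈₀)² / (ln HR)² = 4(1.2816 + 0.8416)² / (0.5621)² = 18.03 / 0.316 = 57.1, rounded up to **58**. This reproduces.

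With exponential PFS, 40 per arm, uniform 16-month accrual and analysis at 20 months, the event probability is 1 − (e^(−4λ) − e^(−20λ)) / (16λ) with λ = ln 2 / median. This gives 0.831 (control) and 0.662 (seribantumab), so 40 × (0.831 + 0.662) = **59.7** events when every progression or death counts. The planned timing thus fits the protocol's definition.

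**2. Power if events are dropped from the 58.** Power = Φ(√d × |ln HR| / 2 − 1.2816), with HR 4/7 (|ln HR| = 0.5596):

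- d = 58: 80.2%
- d = 55: 78.6%
- d = 52: Φ(7.211 × 0.2798 − 1.2816) = Φ(0.736) = 76.9%

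**3. Both rules applied to the same simulated trials.** Inputs from the protocol: 80 patients, 1:1, 16-month accrual, scans every 56 days, one-sided 0.10, cut-off at the 58th event counted under each rule. Assumed: exponential PFS, an unstratified log-rank test, and all stopping rates. Deaths without progression and missed scans are not modelled.

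*(a) No true effect (both medians 4 months); stopping occurs in the 56 days before the scan that would show progression. 20,000 trials per cell, standard error about 0.002. Entries are for 10% v 20% / 10% v 30% stopping (control v seribantumab).*

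| Scans done | Type I error, SAP rule | Type I error, protocol rule | Events lost of 58 |
|---|---|---|---|
| 8-weekly only | 0.127 / 0.173 | 0.099 / 0.102 | 4.0 / 5.4 |
| plus scan at stopping and at 30±7 days | 0.102 / 0.102 | 0.088 / 0.074 | 2.1 / 2.7 |
| plus scan at stopping and at day 28 | 0.090 / 0.080 | 0.085 / 0.070 | 1.0 / 1.3 |

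With the arms reversed and 8-weekly scans only, the SAP rule gives 0.075 / 0.057. Equal stopping of 10% in both arms gives 0.100 to 0.103 under the SAP rule in all three scan sets.

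*(b) Medians 4 v 7; stopping unrelated to progression; scans at stopping and at the follow-up visit done. 10,000 trials per cell, standard error about 0.004. Ranges cover the two visit timings.*

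| Stopping (control v seribantumab) | Events lost of 58 | Delay of 58th event |
|---|---|---|
| 10% v 20% | 3.7 to 4.0 | 1.5 to 1.9 months |
| 15% v 30% | 5.7 to 6.3 | 3.1 to 3.7 months |

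For 15% v 30% with the 30±7-day scan, the median time of the 58th event moves from 20.0 to 23.7 months and power from 0.784 to 0.759. If half of those who stop start new therapy at day 30 (censored under both rules), the losses fall to 2.0–2.2 and 3.2–3.6 events, and the delays to 0.9–1.0 and 2.0–2.3 months.

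**4. Effect on the hazard ratio.** This is a continuous-time approximation at 20 months, with no new therapy before progression. Equal stopping in both arms with no change in hazard leaves the HR at 0.57 under both rules. With stopping of 5% per month on seribantumab and 2% on placebo, and the hazard doubled after stopping, the HR is 0.62 under the protocol rule and 0.60 under the SAP rule. With the hazard tripled it is 0.66 and 0.61. In these cases the SAP rule favours seribantumab.

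**The case against.** **The SAP belongs to another trial.** It opens "This is the Statistical Analysis Plan (SAP) for protocol seribantumab-02-03-10", whereas this protocol is MM-121-02-02-10, and it describes a phase 3, 2:1, 195-event trial with exemestane or fulvestrant. The rule and its four-week note may be right for that protocol. This stands as an explanation and limits what a Table 3.1 edit alone can achieve. It does not remove the conflict, because this is the SAP supplied with the protocol and the rule could be carried into its replacement.

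**The protocol leaves censoring to the SAP.** Section 10.5.1 defers censoring details, and section 10 lets the SAP modify the plans. But the Synopsis already sets out the censoring rules, and section 10 requires major changes to the primary analysis to be reflected in an amendment. Whether a 30-day limit is major is a judgement; since it changes which events count, I would treat it so.

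**Late progressions are not lost altogether.** TTP (SAP 3.4) has no 30-day limit, and late deaths count in OS. That is correct, but both are secondary endpoints. SAP 5.5.2 also lists an interval-censored comparison, without saying that it restores events after day 30.

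**The bias is small when the protocol is followed.** This stands. With the required scans done, type I error under the SAP rule does not exceed 0.10 beyond simulation error. In the 30±7-day case it is the protocol rule that departs from nominal, on the conservative side. Protocol 4.4 and 6.5 place the end-of-treatment visit within 30 days of last dose, which brings the milder day-28 case nearer.

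**The sizes rest on assumptions.** This also stands. The simulation further uses all 80 patients, whereas the protocol's primary set is the smaller per-protocol population.

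**Conclusion.** The concern holds. The contradiction is in the text and needs no assumption: progression or death more than 30 days after stopping, without new therapy or a long scan gap, is an event in the protocol and censored in the SAP. The table note on four weeks also misstates this protocol.

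The main cost is time, or a modest loss of events if the trigger and the analysis use different definitions. Serious bias needs both unequal stopping linked to imminent progression and omission of the required scans; it is possible rather than expected, and its direction is unknown. The conflict should be settled before data are seen, so that nobody later chooses between two versions of the primary result.

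**What to change.** - In a SAP written for MM-121-02-02-10, make primary PFS censoring follow the protocol Synopsis. Remove the treatment-discontinuation row and the 30-day limits, so that progression or death counts regardless of treatment status, subject to the protocol's own rules on new therapy and missed scans.
- Keep the 30-day version as a named sensitivity analysis.
- Delete the four-week note under Table 3.1.
- State that the 58-event trigger uses the same event definition as the analysis.
- Reconcile protocol 4.4, which names one further scan eight weeks after termination, with sections 3.1 and 7.7, which require scans until progression. The 4.4 text can be read as a minimum, but it should say so.
- If the sponsor prefers the 30-day rule as primary, reflect it in a protocol amendment under section 10.

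The cost is wording in a SAP that this trial needs anyway, plus one protocol clarification. The scans are already required, so no new data are needed.
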